10.1.8.1 Protocol amendments

Any change or addition to the protocol can only be made in a written protocol amendment that must be approved by Novartis, health authorities where required, and the IRB/IEC prior to implementation.

Only amendments that are required for participant safety may be implemented immediately provided the health authorities are subsequently notified by protocol amendment and the reviewing IRB/IEC is notified.

Notwithstanding the need for approval of formal protocol amendments, the Investigator is expected to take any immediate action required for the safety of any participant included in this study, even if this action represents a deviation from the protocol. In such cases, Novartis should be notified of this action and the IRB/IEC at the study site should be informed according to local regulations.

10.2 Appendix 2: Abbreviations and definitions

10.2.1 List of abbreviations

ADR	Adverse Drug Reaction
AE	Adverse Event
ALP	Alkaline Phosphatase
ALT	Alanine Aminotransferase
ANA	Antinuclear Antibodies
ANCOVA	Analysis of covariance
ApoA-1	Apolipoprotein A-1
ApoB	Apolipoprotein B
APTT	Activated Partial Thromboplastin time
ASCVD	Atherosclerotic Cardiovascular Disease
ASGPR	Asialoglyco Protein Receptors
ASMA	Anti-smooth muscle antibody
ASO	Antisense Oligonucleotide
AST	Aspartate Aminotransferase
ATC	Anatomical Therapeutic Chemical
BP	Blood pressure
BUN	Blood Urea Nitrogen
CFR	Code of Federal Regulations
CIOMS	Council for International Organizations of Medical Sciences
CK	Creatine Kinase
cm	centimeter(s)
CMO&PS	Chief Medical Office and Patient Safety
CMV	Cytomegalovirus
CO	Country Organization
COA	Clinical Outcome Assessment
CRA	Clinical Research Associate
CRF	Case Report/Record Form (paper or electronic)
CRO	Contract Research Organization
CSR	Clinical study report
CTIS	Clinical Trials Information System
CTT	Clinical Trial Team
CV	Cardiovascular
CVD	Cardiovascular Disease
DBP	Diastolic Blood Pressure
DHA	Docosahexaenoic acid
DILI	Drug-Induced Liver Injury
dL	deciliter(s)
DLT	Dose Limiting Toxicity
DNA	Deoxyribonucleic acid
EBV	Epstein-Barr virus
ECG	Electrocardiogram
eCRF	electronic Case Report Forms
EDC	Electronic Data Capture
eGFR	Estimated glomerular filtration rate

EMA	European Medicines Agency
EOC	End of core part
EOS	End of Study
EPA	Eicosapentaenoic acid
ERCP	Endoscopic retrograde cholangiopancreatography
eSAE	Electronic Serious Adverse Event
EU	European Union
EudraCT	European Union Drug Regulating Authorities Clinical Trials Database
FAS	Full Analysis Set
FDA	Food and Drug Administration
FPG	Fasting Plasma Glucose
FSH	Follicle Stimulating Hormone
GalNAc	N-Acetylgalactosamine
GCP	Good Clinical Practice
GCS	Global Clinical Supply
GGT	Gamma-glutamyl transferase
GLDH	Glutamate Dehydrogenase
h	Hour
HAV	Hepatitis A Virus
HbA1c	Glycated hemoglobin (hemoglobin A1c)
HBsAg	Hepatitis B virus surface antigen
HBV	Hepatitis B Virus
HCV	Hepatitis C Virus
HDL-C	High-Density Lipoprotein Cholesterol
HeFH	Heterozygous Familial Hypercholesterolemia
HEV	Hepatitis E Virus
HIV	Human immunodeficiency virus
HSV	Herpes simplex virus
HTN	Hypertension
IB	Investigator's Brochure
ICF	Informed Consent Form
ICH	International Council for Harmonization of Technical Requirements for Pharmaceuticals for Human Use
IEC	Independent Ethics Committee
IN	Investigator Notification
INR	International Normalized Ratio
IRB	Institutional Review Board
IRT	Interactive Response Technology
ITT	Intent-To-Treat
IUD	Intrauterine Device
IUS	Intrauterine System
LDL-C	Low-Density Lipoprotein Cholesterol
LDLR	Low Density Lipoprotein Receptor
LFT	Liver function test
LLT	Lipid-Lowering Therapy
Lp(a)	Lipoprotein (a)
LPLV	Last participant last visit

MACE	Major adverse cardiovascular event
MCH	Mean Corpuscular Hemoglobin
MCHC	Mean Corpuscular Hemoglobin Concentration
MCV	Mean Corpuscular Volume
MedDRA	Medical dictionary for regulatory activities
mg	milligram(s)
mL	milliliter(s)
MRI	Magnetic resonance imaging
mRNA	Messenger ribonucleic acid
non-HDL-C	non-High-Density Lipoprotein Cholesterol
PCR	Protein-creatinine ratio
PCSK9	Proprotein Convertase Subtilisin/Kexin type 9
PD	Pharmacodynamic(s)
PDC	Proportion of days covered
PFS	Prefilled syringe
PMM	Pattern-Mixture Model
PT	prothrombin time
R Value	ALT/ALP x ULN
RAS	Randomized Set
RDO	Retrieved Drop Out
RISC	Ribonucleic acid-Induced Silencing Complex
RNA	Ribonucleic acid
s.c.	subcutaneous
SAE	Serious Adverse Event
SAF	Safety Analysis Set
SAP	Statistical Analysis Plan
SARS-CoV- 2	Severe acute respiratory syndrome coronavirus 2 also referred to as COVID-19
SBP	Systolic Blood Pressure
SCR	Screened Set
siRNA	small interfering RNA
SoA	Schedule of Activities
SUSAR	Suspected Unexpected Serious Adverse Reaction
TBL	Total bilirubin
TC	Total cholesterol
TEAE	Treatment-Emergent Adverse Event
TG	Triglycerides
ULN	upper limit of normal
WHO	World Health Organization

10.2.2 Definitions

Additional treatment	Medicinal products that may be used during the clinical trial as described in the protocol, but not as an investigational medicinal product (e.g. any background therapy)
Assessment	A procedure used to generate data required by the study
Biologic Samples	A biological specimen including, for example, blood (plasma, serum), saliva, tissue, urine, stool, etc. taken from a study participant
Clinical Trial Team	A group of people responsible for the planning, execution and reporting of all clinical trial activities. Examples of team members include the Study Lead, Medical Monitor, Trial Statistician etc.

Coded Data	Personal Data which has been de-identified by the investigative center team by replacing personal identifiers with a code.
Control drug	A study intervention (active or placebo) used as a comparator to reduce assessment bias, preserve blinding of investigational drug, assess internal study validity, and/or evaluate comparative effects of the investigational drug
Discontinuation from study	Point/time when the participant permanently stops receiving the study treatment and further protocol required assessments or follow-up, for any reason. No specific request is made to stop the use of their samples or data.
Discontinuation from study treatment	Point/time when the participant permanently stops receiving the study treatment for any reason (prior to the planned completion of study intervention administration, if any). Participant agrees to the other protocol required assessments including follow-up. No specific request is made to stop the use of their samples or data.
Dosage	Dose of the study treatment given to the participant in a time unit (e.g. 100 mg once a day, 75 mg twice a day)
Electronic Data Capture (EDC)	Electronic data capture (EDC) is the electronic acquisition of clinical study data using data collection systems, such as Web-based applications, interactive voice response systems and clinical laboratory interfaces. EDC includes the use of Electronic Case Report Forms (eCRFs) which are used to capture data transcribed from source data/documents used at the point of care
End of the clinical trial	The end of the clinical trial is defined as the last visit of the last participant.
Enrollment	Point/time of participant entry into the study at which informed consent must be obtained. The action of enrolling one or more participants
Estimand	As defined in the ICH E9(R1) addendum, estimand is a precise description of the treatment effect reflecting the clinical question posed by the trial objective. It summarizes at a population-level what the outcomes would be in the same participants under different treatment conditions being compared. Attributes of an estimand include the population, variable (or endpoint) and treatment of interest, as well as the specification of how the remaining intercurrent events are addressed and a population-level summary for the variable.
Intercurrent events	Events occurring after treatment initiation that affect either the interpretation or the existence of the measurements associated with the clinical question of interest.
Investigational drug/ treatment	The drug whose properties are being tested in the study
Investigational Medical Device	Medical Device being assessed for safety or performance in a clinical investigation. This includes devices already on the market and being evaluated for new intended uses, new populations, new materials, or design changes
Medication number	A unique identifier on the label of medication kits
Mis-randomized participants	Mis-randomized participants are those who were not qualified for randomization and who did not take study treatment, but have been inadvertently randomized into the study or the participant allocated to an invalid stratification factor
Other treatment	Treatment that may be needed/allowed during the conduct of the study (i.e. concomitant or rescue therapy)
Participant	A trial participant (can be a healthy volunteer or a patient). "Participant" terminology is used in the protocol whereas term "Subject" is used in data collection
Participant number	A unique number assigned to each participant upon signing the informed consent. This number is the definitive, unique identifier for the participant and should be used to identify the participant throughout the study for all data collected, sample labels, etc.
Period	The subdivisions of the trial design (e.g. Screening, Treatment, Follow-up) which are described in the Protocol. Periods define the study phases and will be used in clinical trial database setup and eventually in analysis
Personal data	Participant information collected by the Investigator that is coded and transferred to Novartis for the purpose of the clinical trial. This data includes participant identifier information, study information and biological samples.

Randomization	The process of assigning trial participants to investigational drug or control/comparator drug using an element of chance to determine the assignments in order to reduce bias.
Randomization number	A unique identifier assigned to each randomized participant
Remote	Describes any trial activities performed at a location that is not the investigative site.
Rescreening	If a participant fails the initial screening and is considered as a Screen Failure, he/she can be invited once for a new Screening visit after medical judgment and as specified by the protocol
Screen Failure	A participant who did not meet one or more criteria that were required for participation in the study
Source Data/Document	Source data refers to the initial record, document, or primary location from where data comes. The data source can be a database, a dataset, a spreadsheet or even hard-coded data, such as paper or eSource
Start of the clinical trial	The start of the clinical trial is defined as the signature of the informed consent by the first participant
Study treatment	Any drug or combination of drugs or intervention administered to the study participants as part of the required study procedures; includes investigational drug(s), control(s) or background therapy
Tele-visit	Procedures or communications conducted using technology such as telephone or video-conference, whereby the participant is not at the investigative site where the Investigator will conduct the trial.
Treatment arm/group	A treatment arm/group defines the dose and regimen or the combination, and may consist of 1 or more cohorts.
Treatment of interest	The treatment of interest and, as appropriate, the alternative treatment to which comparison will be made. These might be individual interventions, combinations of interventions administered concurrently, e.g. as add-on to standard of care, or might consist of an overall regimen involving a complex sequence of interventions. This is the treatment of interest used in describing the related clinical question of interest, which might or might not be the same as the study treatment.
Variable (or endpoint)	The variable (or endpoint) to be obtained for each participant that is required to address the clinical question. The specification of the variable might include whether the participant experiences an intercurrent event.
Withdrawal of consent	Withdrawal of consent from the study occurs when the participant explicitly requests to stop use of their data and/or biological samples AND no longer wishes to receive study treatment, AND does not agree to further protocol required assessments. This request should be in writing (depending on local regulations) and recorded in the source documentation. This request should be distinguished from a request to discontinue the study. Other study participant's privacy rights are described in the corresponding informed consent form.

10.3 Appendix 3: Clinical laboratory tests

10.3.1 Clinically notable laboratory values and vital signs

The central laboratory will flag laboratory values falling outside of the normal ranges on the central laboratory reports. Investigators are responsible for reviewing these abnormal values for clinical significance, signing the laboratory reports to indicate their review, and reporting values considered clinically significant in the appropriate eCRF.

Any clinically significant abnormal laboratory value should be evaluated and followed-up by the investigator until normal or a cause for the abnormality is determined.

10.4 Appendix 4: Participant Engagement

The following participant engagement initiatives are included in this study and will be provided, as available, for distribution to study participants at the time points indicated. If compliance is impacted by cultural norms or local laws and regulations, sites may discuss modifications to these requirements with Novartis.

- Thank You letter
- Plain language trial summary - after Clinical study report (CSR) publication
- Individual study results - after CSR publication

10.5 Appendix 5: Liver safety monitoring

To ensure participant safety and enhance reliability in determining the hepatotoxic potential of an investigational drug, a standardized process for identification, monitoring and evaluation of liver events has to be followed.

Please refer to [Table 10-1](#) in [Section 10.5](#) for complete definitions of liver laboratory triggers.

Once a participant is exposed to study treatment, every liver event defined in [Table 10-1](#) should be followed up by the Investigator or designated personnel at the trial site, as summarized below. Additional details on actions required in case of liver events are outlined in [Table 10-2](#). Repeat liver chemistry tests (i.e. ALT, AST, TBL, PT/INR, ALP and G-GT) to confirm elevation.

- These liver chemistry repeats will be performed using the central laboratory. If results will not be available from the central laboratory, then the repeats can also be performed at a local laboratory to monitor the safety of the participant. If a liver event is subsequently reported, any local liver chemistry tests previously conducted that are associated with this event should have results recorded on the appropriate CRF.
- If the initial elevation is confirmed, close observation of the participant will be initiated, including consideration of treatment interruption if deemed appropriate.
- Discontinuation of the investigational drug (refer to the Discontinuation of study treatment section), if appropriate
- Hospitalization of the participant if appropriate
- Causality assessment of the liver event
- Thorough follow-up of the liver event should include
 - These investigations can include based on Investigator's discretion: serology tests, imaging and pathology assessments, hepatologist's consultancy; obtaining more detailed history of symptoms and prior or concurrent diseases, history of concomitant drug use, exclusion of underlying liver disease

All follow-up information and procedures performed must be recorded as appropriate in the CRF.

10.5.1 Liver event and laboratory trigger definitions & follow-up requirements

Table 10-1 Liver event and laboratory trigger definitions

Definition/ threshold	
Liver laboratory triggers If ALT, AST and total bilirubin normal at baseline:	
 • ALT or AST > 5 × ULN • ALP > 2 × ULN (in the absence of known bone pathology) • Total bilirubin > 3 × ULN (in the absence of known Gilbert syndrome) • ALT or AST > 3 × ULN and INR > 1.5 • Potential Hy's Law cases (defined as ALT or AST > 3 × ULN and Total bilirubin > 2 × ULN [mainly conjugated fraction] without notable increase in ALP to > 2 × ULN) • Any clinical event of jaundice (or equivalent term) • ALT or AST > 3 × ULN accompanied by (general) malaise, fatigue, abdominal pain, nausea, or vomiting, or rash with eosinophilia • Any adverse event potentially indicative of a liver toxicity
If ALT or AST abnormal at baseline:	• ALT or AST > 3x baseline or > 300 U/L (whichever occurs first)

Table 10-2 Follow up requirements for liver laboratory triggers - ALT, AST, TBL

ALT	TBL	Liver Symptoms	Action
ALT increase without bilirubin increase:			
If normal at baseline: ALT > 3 x ULN	Normal For participants with Gilbert's syndrome: No change in baseline TBL	None	
 No change to study treatment Measure ALT, AST, ALP, GGT, TBIL, INR, albumin, CK, and GLDH in 48-72 hours. Follow-up for symptoms.
If elevated at baseline: ALT > 2 x baseline or > 300 U/L (whichever occurs first)			
If normal at baseline: ALT > 5 x ULN for more than two weeks	Normal For participants with Gilbert's syndrome: No change in baseline TBL	None	
 Interrupt study treatment Measure ALT, AST, ALP, GGT, TBIL, INR, albumin, CK, and GLDH in 48-72 hours. Follow-up for symptoms. Initiate close monitoring and workup for competing etiologies. Study treatment can be restarted only if another etiology is identified and liver enzymes return to baseline.
If elevated at baseline: ALT > 3 x baseline AND >5x ULN for more than two weeks			
If normal at baseline: ALT > 8 x ULN	Normal	None	
ALT increase with bilirubin increase:			
If normal at baseline: ALT > 3 x ULN	TBL > 2 x ULN (or INR > 1.5) For participants with Gilbert's syndrome: Doubling of direct bilirubin	None	
If elevated at baseline: ALT > 2 x baseline AND >3x ULN			
If normal at baseline: ALT > 3 x ULN	Normal or elevated	Severe fatigue, nausea, vomiting, right upper quadrant pain	
If elevated at baseline: ALT > 2 x baseline AND >3x ULN, OR ALT > 300 U/L			

Table 10-3 Follow up requirements for liver laboratory triggers - Isolated Hyperbilirubinemia

Criteria	Actions required	Follow-up monitoring
Total Bilirubin (isolated)		
>1.5 – 3.0 ULN	
 Maintain treatment Repeat LFTs within 48-72 hours 	Monitor LFTs weekly until resolution to ≤ Grade 1 or to baseline
> 3 - 10 x ULN (in the absence of known Gilbert syndrome)	
 Interrupt treatment Repeat LFT within 48-72 hours Hospitalize if clinically appropriate Establish causality Record the AE and contributing factors (e.g. conmeds, med hx, lab) in the appropriate CRF 	Monitor LFTs weekly until resolution to ≤ Grade 1 or to baseline (ALT, AST, total bilirubin, Alb, PT/INR, ALP and GGT) Test for hemolysis (e.g. reticulocytes, haptoglobin, unconjugated [indirect] bilirubin)
> 10 x ULN	
 Discontinue the study treatment immediately Hospitalize the participant Establish causality Record the AE and contributing factors (e.g. 	ALT, AST, total bilirubin, Alb, PT/INR, ALP and GGT until resolution (frequency at Investigator discretion)

Criteria	Actions required	Follow-up monitoring
Any AE potentially indicative of a liver toxicity	
conmeds, med hx, lab)in the appropriate CRF
 
• Consider study treatment interruption or discontinuation• Hospitalization if clinically appropriate• Establish causality• Record the AE and contributing factors(e.g. conmeds, med hx, lab)in the appropriate CRF	Investigator discretion

Based on Investigator's discretion investigation(s) for contributing factors for the liver event can include: Serology tests, imaging and pathology assessments, hepatologist's consultancy; obtaining more detailed history of symptoms and prior or concurrent diseases, history of concomitant drug use, exclusion of underlying liver disease.

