6.5.2.1 Follow up on potential drug-induced liver injury (DILI) cases

Participants with transaminase increase combined with total bilirubin increase may be indicative of potentially severe DILI and should be considered as clinically important events and assessed appropriately to establish the diagnosis. The required clinical information, as detailed below, should be sought to obtain the medical diagnosis of the most likely cause of the observed laboratory abnormalities.

The threshold for potential DILI may depend on the participant's baseline AST/ALT and total bilirubin value; participants meeting any of the following criteria will require further follow-up as outlined below:

- For participants with normal ALT and AST and total bilirubin value at baseline: AST or ALT $> 3.0 \times$ ULN combined with total bilirubin $> 2.0 \times$ ULN
- For participants with elevated AST or ALT or total bilirubin value at baseline: [AST or ALT $> 2 \times$ baseline] OR [AST or ALT $> 300 \text{ U/L}$], whichever occurs first combined with [total bilirubin $> 2 \times$ baseline AND $> 2.0 \times$ ULN]

As DILI is essentially a diagnosis of exclusion, other causes of abnormal liver tests should be considered and their role clarified before DILI is assumed to be the cause of liver injury.

A detailed history, including relevant information such as review of ethanol consumption, concomitant medications, herbal remedies, supplement consumption, history of any pre-existing liver conditions or risk factors, should be collected.

Laboratory tests should include ALT, AST, total bilirubin, direct and indirect bilirubin, Gamma-glutamyl transferase (GGT), prothrombin time (PT)/International Normalized Ratio (INR), alkaline phosphatase, albumin, and creatine kinase. If available, testing of Glutamate Dehydrogenase (GLDH) is additionally recommended.

Perform relevant examinations (Ultrasound or Magnetic resonance imaging (MRI), Endoscopic retrograde cholangiopancreatography (ERCP)) as appropriate, to rule-out an extrahepatic cause of cholestasis. Cholestasis (is defined as an Alkaline Phosphatase (ALP) elevation $> 2.0 \times$ ULN with R value < 2 in participants without bone metastasis, or elevation of the liver-specific ALP isoenzyme in participants with bone metastasis).

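### Protocol Table 10-2 requires liver retests at ALT levels below the Table 10-1 triggers, and the Table 10-1 row for a raised baseline has no combined ALT-bilirubin criterion

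*Protocol*

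**What the plan says.** Protocol Section 10.5 sends the site to Table 10-1 "for complete definitions of liver laboratory triggers". It then says that every liver event defined in that table "should be followed up by the Investigator or designated personnel at the trial site, as summarized below". Table 10-2 has a dependent role: "Additional details on actions required in case of liver events are outlined in" that table, and its title is "Follow up requirements for liver laboratory triggers - ALT, AST, TBL".

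For ALT, AST and bilirubin all normal at baseline, the Table 10-1 criterion for an isolated transaminase rise is "ALT or AST > 5 × ULN". The combined criteria (with INR, with bilirubin as a potential Hy's Law case, with symptoms) are listed in the same row. For ALT or AST abnormal at baseline there is one criterion: "ALT or AST > 3x baseline or > 300 U/L (whichever occurs first").

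The lowest tier of Table 10-2 covers ALT rises with normal bilirubin and no symptoms. It starts above 3 x ULN for a normal baseline. For a raised baseline it reads "If elevated at baseline: ALT > 2 x baseline or > 300 U/L (whichever occurs first"). The action is a repeat panel in 48-72 hours and symptom follow-up, with study treatment unchanged. A separate raised-baseline row covers ALT above both 2 x baseline and 3 x ULN with bilirubin above 2 x ULN (or INR above 1.5).

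Section 6.5.2.1 sets laboratory criteria for potential DILI. It groups baselines differently: "For participants with elevated AST or ALT or total bilirubin value at baseline", the criterion is a transaminase above 2 x baseline or above 300 U/L, together with bilirubin above both 2 x baseline and 2 x ULN.

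**The concern.** If Table 10-1 defines the events and Table 10-2 only says what to do about them, nothing should need action under Table 10-2 that is not an event under Table 10-1. Some results do. A site that follows Section 10.5 in order and finds no Table 10-1 trigger has no stated reason to go on to Table 10-2, and could miss a retest that Table 10-2 requires.

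The more serious case is a participant with raised baseline ALT or AST who later has raised ALT and raised bilirubin together. Table 10-2 and Section 6.5.2.1 both address that combination; the Table 10-1 row for that participant does not.

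Scheduled visits are about 30 to 60 days apart, so a missed 48-72 hour repeat is not soon replaced. The SAP's liver summaries (Section 2.7.3) include unscheduled tests, and Section 2.7.1.1 summarises hepatotoxicity as an event of special interest, so uneven site practice could reach the safety tables.

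**Working it through.** The plan gives no figure to reproduce. The check compares the two tables' rules over ALT values.

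**Inputs.** B is baseline ALT in U/L. The documents give no ULN in U/L, so 40 is assumed and varied from 30 to 55.

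| Situation | Table 10-1 | Table 10-2 |
|---|---|---|
| Normal baseline; isolated rise, no symptoms, normal bilirubin | > 5 x ULN | > 3 x ULN |
| Raised baseline; same | > 3 x B or > 300 | > 2 x B or > 300 |
| Raised baseline; bilirubin > 2 x ULN | no combined criterion; > 3 x B or > 300 only | > 2 x B and > 3 x ULN |

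**1. Normal baseline, isolated rise.** The gap is 3 x ULN < ALT <= 5 x ULN.
- ULN 30: above 90 up to 150, so 91-150 U/L
- ULN 40: above 120 up to 200, so 121-200 U/L
- ULN 55: above 165 up to 275, so 166-275 U/L

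**2. Raised baseline, isolated rise.** The gap is 2B < ALT <= the smaller of 3B and 300.
- B = 60: above 120 up to 180, so 121-180 U/L
- B = 80: above 160 up to 240, so 161-240 U/L
- B = 120: above 240 up to 300 (3B = 360, capped), so 241-300 U/L

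The gap closes when 2B reaches 300, that is at B = 150 or more. A baseline of 60 exceeds every ULN in the assumed range, so its gap does not depend on which of those values is used. Exclusion criterion 5 rules out unexplained ALT or AST only above 3 x ULN (120 U/L at ULN 40), so such baselines can enrol.

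**3. Reverse direction.** In steps 1 and 2 no ALT value meets Table 10-1 without also meeting Table 10-2: 5 x ULN exceeds 3 x ULN, 3B exceeds 2B, and both tables share the 300 U/L limit.

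**4. Raised baseline with raised bilirubin.** Take B = 60, ULN = 40, current ALT 150 and bilirubin 2.5 x ULN.
- Table 10-2: 150 > 2 x 60 = 120, 150 > 3 x 40 = 120, and 2.5 > 2. Met.
- Section 6.5.2.1: 150 > 120 and 2.5 > 2. Met if bilirubin has also more than doubled, that is if baseline bilirubin was below 2.5 / 2 = 1.25 x ULN.
- Table 10-1, abnormal-baseline row: 150 is not above 3 x 60 = 180 and not above 300. Not met.

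In general the gap is the larger of 2B and 3 x ULN, up to the smaller of 3B and 300. For B = 60 this is 121-180 U/L at ULN 30 or 40, and 166-180 U/L at ULN 55.

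**5. Baseline grouping.**

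| Raised at baseline | Table 10-1 row | Section 6.5.2.1 group |
|---|---|---|
| None | normal | normal |
| ALT or AST | abnormal | elevated |
| Bilirubin only | none | elevated |

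**The case against.** The strongest reply is that the tables form a tiered scheme: Table 10-1 names liver events, and the action tables begin lower with an early-watch tier. Table 10-3 has the same shape. It acts on isolated bilirubin from above 1.5 x ULN with treatment maintained, while Table 10-1 lists bilirubin only above 3 x ULN. This reading is plausible, but no passage states it, and Section 10.5 says the opposite by calling Table 10-1 complete and tying Table 10-2 to events.

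A reader might infer that the tables give incompatible orders, or that a site never reaches the lower rows of Table 10-2 and so would miss the retest. The documents do not support that. Step 3 shows that a site can satisfy both tables for isolated rises. Each Table 10-2 row also carries its own condition and action, and the tables stand together in Section 10.5.1. Section 10.3.1 has the central laboratory flag abnormal values and the investigator review them, so such values would not go unseen, although that does not secure the 48-72 hour timing. What stands is that a retest could be missed.

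The Table 10-1 entry for any adverse event suggesting liver toxicity does not close the gap. It is printed under the normal-baseline row, and Section 8.6.1 makes a laboratory value an adverse event only if it causes symptoms, is judged clinically significant or needs therapy. Section 6.5.2.1 does catch many of the combined cases in step 4, but no isolated rises.

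For a normal baseline, Table 10-1 already triggers above 3 x ULN with INR above 1.5, with the listed symptoms or as a potential Hy's Law case. The step 1 gap is therefore confined to isolated, asymptomatic rises. If the sponsor meant those combined criteria to apply whatever the baseline, the step 4 gap would largely close, but the table as printed does not say so.

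**Conclusion.** The inconsistency is real and should be corrected. For isolated, asymptomatic rises with normal bilirubin, Table 10-2 asks for a retest over a band of ALT values that are not Table 10-1 laboratory triggers: 3 to 5 x ULN for a normal baseline, and 2 to 3 x baseline (capped at 300 U/L) for a raised one. The consequence in that band is a repeat panel with treatment unchanged. The raised-baseline row of Table 10-1 also omits the ALT-bilirubin combination, and a participant with only bilirubin raised at baseline has no row.

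The U/L ranges rest on an assumed ULN; the multiples do not. Merged table cells make it uncertain which action belongs to the combined row of Table 10-2, so nothing here depends on that action.

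Three further inferences go too far. Raised baselines can occur under exclusion criterion 5, but the documents give no frequency, so one cannot say that they will. Ascertainment could vary between sites through unscheduled tests and reported events, but the SAP's liver tables apply fixed cut-offs, including 3 x ULN, regardless of Table 10-1 status. The primary efficacy analysis is not affected.

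**What to change.** Reconcile Section 10.5, Tables 10-1 and 10-2, and Section 6.5.2.1:
- Use one baseline grouping throughout, with a place for a participant whose only raised baseline value is bilirubin.
- Either align the trigger and action thresholds, or state that the Table 10-2 rows apply even when no Table 10-1 trigger is met.
- State how the combined ALT-bilirubin criterion applies in Table 10-1 when baseline ALT or AST is raised.

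The choice of thresholds belongs to the sponsor; no view is taken here on which is right. The cost is a protocol wording amendment.
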